8.2.3. Sample Size Re-estimation

The aggregate blinded event-rate data will be periodically reviewed by the Executive Committee and the sponsor. The study has an event-driven design. Should emerging data diverge significantly from protocol assumptions, the total sample size and/or follow up time may be adjusted, within the bounds of feasibility, to achieve the event target.

8.3. Data Analysis Considerations**8.3.1. Analysis Populations**

The intent-to-treat (ITT) population will include all randomly assigned subjects. The ITT subjects will be analyzed according to randomised treatment. The inference for primary objectives in the study will be made from ITT population.

Per-protocol Population (PP) will exclude the subjects who have major protocol violations. Per-protocol analysis will include Per-protocol population only and their data upon to the time of discontinuation of investigational product plus 56 days.

The non-insulin population (NI) will include all subjects in the ITT population who are not on insulin at baseline. Inference for the time to insulin endpoint will be made from the NI population.

The baseline basal insulin user population (BI) will include all subjects in the ITT population who are on basal insulin, but not on other insulin at baseline. Inference for the time to prandial insulin endpoint will be made on BI population.

The safety population will include all enrolled subjects who receive at least 1 dose of study treatment. The safety population subjects will be analyzed according to the treatment received. The safety population will be used for analyses of safety objectives.

Other analysis populations will be defined in the RAP.

8.3.2. Analysis Data Set

For time to event data, censoring time for subjects who lost to follow-up is defined as following:

- For primary analysis, subjects who are lost to follow-up will be censored at the date of last evidence of confirmatory status for MACE events.
- For on-treatment analysis, censoring date will be the last dose date.
- For on-therapy analysis (on-treatment+56 days), censoring date will be the last dose date+56 days.
- For analysis of all cause of mortality, censoring date will be the latest date known alive.

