The investigational product (albiglutide and albiglutide matching placebo) must be stored in a secure area at 2°C to 8°C and protected from freezing. Each site must maintain a temperature log. Access to and administration of the investigational product will be limited to the investigator and authorised site staff (investigator or designee). Investigational product must be dispensed or administered only to subjects enrolled in the study and in accordance with the protocol.

Procedures for the disposal of unused study treatment will be provided in the SRM.

Investigational product (albiglutide or albiglutide matching placebo) will be administered once weekly by subcutaneous injection. The first dose is to be administered at the clinic. The starting dose of albiglutide will be 30 mg once weekly. If at any stage after 5 weeks of treatment in the opinion of the investigator the subject needs to have intensified therapy to improve glycaemic control, the dose of investigational product should be increased before altering the doses of other glucose-lowering medication. In this case the subject will be called in for an unscheduled visit to supervise an increase in dose from 30 mg to 50 mg. Subjects randomly assigned to albiglutide matching placebo will also go through the increased dose procedure to maintain study blind. If a subject experiences tolerability issues with the higher, 50mg dose then the investigator may decrease the dose back to 30 mg without the need for an unscheduled visit to supervise down titration, other than for the subject to collect pens of the correct dose.

Albiglutide (or albiglutide matching placebo) may be administered at any time of day without regard to meals. Preferably, it should be administered once a week on the same day each week. The day of weekly administration can be changed if necessary as long as the last dose was administered 4 or more days previously. If a dose is missed, it should be administered as soon as possible within 3 days after the missed dose. Thereafter, subjects can resume dosing on their usual day of administration. If it is more than 3 days after the missed dose, subjects should wait and administer their next regularly scheduled weekly dose.

If a subject misses 4 or more consecutive doses, the investigator should contact the medical monitor to discuss options for helping assure better compliance.

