8.3.6.1. Primary Analysis

The primary analysis is an ITT analysis of the time to the first occurrence of MACE over the full duration of the study. Time to event analyses will be performed using Cox's Proportional Hazard regression with SAS PHREG with treatment group as the only covariate. Data for subjects without a primary event will be censored.

Treatment differences will be estimated via the hazard ratio and its 95% confidence interval (CI).

The hypothesis of non-inferiority of albiglutide relative to placebo group with hazard ratio less than 1.3 with respect to cardiovascular risk will be tested at the end of the study when ~611 first MACE events are cumulated.

The strength of evidence for non-inferiority will be determined by testing the hypothesis that the observed hazard ratio is significantly different from the null margin of 1.3 (one-sided $p < 0.025$ for such a test being equivalent to the upper 95% confidence limit after multiplicity adjustment for the hazard ratio being less than 1.3). The absolute risk difference per 100 PY and superiority p-value for albiglutide vs. placebo will also be presented.

The product-limit estimates of the probabilities (and their standard errors) of first MACE over time will be computed and displayed as Kaplan-Meier (KM) survival curves for albiglutide and placebo groups. The KM curves will also be presented corresponding to the above comparisons.

The total number of all MACE or any of its components will be analyzed by Poisson regression model. The incidence rate per 100 person-years, relative risk and their 95% CI will be presented. Number of subjects who experienced at least one event, 2 or 3 or more MACE or its components will also be summarized by treatment group.

As sensitivity analyses, the analyses described above will be repeated using events occur while on-treatment and events occur during the period of on-treatment plus 56 days post last dose.

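### The on-treatment sensitivity analysis closes on the last dose date of a weekly injection, so about 6 in 7 fatal first MACE in patients still dosing fall outside it

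*Protocol*

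**What the plan says.** Protocol Section 8.3.2 lists censoring dates under the lead-in "For time to event data, censoring time for subjects who lost to follow-up is defined as following". Two items matter here:

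- "For on-treatment analysis, censoring date will be the last dose date"
- "For on-therapy analysis (on-treatment+56 days), censoring date will be the last dose date+56 days"

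Section 8.3.6.1 makes the primary analysis ITT over the full study. It then adds, as sensitivity analyses, that "the analyses described above will be repeated using events occur while on-treatment", and again for on-treatment time plus 56 days counted from the last dose. Section 8.3.1 defines a per-protocol analysis that also runs to 56 days after discontinuation.

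On dosing, Section 5.1 says that the product "will be administered once weekly by subcutaneous injection". It also sets the flexibility around that interval: "The day of weekly administration can be changed if necessary as long as the last dose was administered 4 or more days previously", and "If a dose is missed, it should be administered as soon as possible within 3 days after the missed dose". Section 5.7 gives a half-life of about 5 days, with therapeutic concentrations lasting 3 to 4 weeks after the drug is stopped. Section 2 defines MACE as cardiovascular death, myocardial infarction or stroke.

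The wording of Section 8.3.2 is the same in the original protocol and in Amendment 1. The list of Amendment 2 changes in Appendix 9 does not touch it.

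**The concern.** With weekly dosing, the last dose date is not the end of exposure. An adherent patient is ordinarily 0 to 6 days past an injection. For someone who has a non-fatal MI or stroke and goes on injecting, the last dose comes later and the event is counted. For someone who dies, the last dose is the injection before death, so the patient is censored before the event unless death falls on an injection day. The same happens when a non-fatal event ends dosing for good.

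The loss is therefore selective. It falls on cardiovascular death and on events that end dosing, in patients who by the protocol's own pharmacokinetic figures are still exposed. The narrowest exposure-based check on the ITT result would be nearly blind to one of the three MACE components. Section 8.3.6.1 also repeats the Poisson analysis of MACE and its components on treatment, so an on-treatment analysis of cardiovascular death would be close to empty.

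**Working it through.** **The plan's own figure first.** Section 8.2.1 states 611 events for 90% power to rule out 1.3 at a true hazard ratio of 1.0, one-sided 0.025, with 1:1 allocation. Schoenfeld: 4 × (1.960 + 1.282)² / (ln 1.3)² gives 611, and power at 611 events is 0.900. This reproduces, so the same formula is used for power below.

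**Where the window closes.** Section 8.3.2 equates on-treatment + 56 days with last dose date + 56 days. Subtracting 56 days from both sides, on-treatment ends on the last dose date. The matching phrase in Section 8.3.6.1 also counts the 56 days from the last dose.

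**Share of deaths after the window.** Let the dosing interval be L days, with death equally likely on each day and a death dated on the injection day counted as on treatment. The share lost is (L − 1)/L.

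| Interval | Source in Section 5.1 | Share lost |
|---|---|---|
| L = 4 | shortest gap when the dosing day is changed | 3/4 = 75% |
| L = 7 | weekly schedule | 6/7 = 86% |
| L = 10 | 7 + 3 days, late dose | 9/10 = 90% |

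Two variants:

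- If 5% to 20% of weekly doses are skipped (assumed), the share is 1 − (1 − q)/7, which is 86.4% to 88.6%.
- If a death on the usual injection day may come before that day's injection, about half of those deaths are lost as well: 1 − 0.5/7 = 92.9%. A simulation of 400,000 deaths on calendar dates gave the same 92.9%.

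**Residual exposure.** With a 5-day half-life, the fraction of a dose remaining after 6 days is 0.5^(6/5) = 44%.

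**Effect on event count and power (illustration).** The documents do not give the fatal share f of on-drug first MACE, so f = 10% to 40% is assumed. Non-fatal events that end dosing are ignored here. Share dropped = f × 6/7, which is 8.6% (f = 10%) to 34.3% (f = 40%). The number of on-drug events D is also assumed.

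| D | Power with none lost | Events lost, f = 10% to 40% | Power with loss |
|---|---|---|---|
| 611 | 90% | 52 to 209 | 87% to 75% |
| 450 | 79% | 39 to 154 | 76% to 62% |

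**Effect of extending the window.** Last dose + 7 days covers every death in patients on a strict weekly schedule. In a 10-day interval it misses days 8 and 9, or 2/10 of deaths. Last dose + 10 days covers these too. The planned +56-day analysis loses essentially none among patients dosing on schedule.

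**The case against.** **The lead-in.** The list is introduced as applying to subjects lost to follow-up, and a patient with an adjudicated fatal event is not lost to follow-up. Section 8.3.6.1 says that subjects without a primary event are censored and does not refer back to Section 8.3.2. On a literal reading the rule never reaches deaths. That reading is possible but leaves no on-treatment window for anyone else. The items for the two exposure windows carry no such restriction, and both sections count the 56 days from the last dose. The lead-in needs correcting on either reading.

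**The analysis plan may settle it.** Details are deferred to the RAP, which is not shown and could add a dosing interval. But the protocol is not silent here: it names a date, and the date is unsuitable.

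**Other analyses cover the ground.** This stands, and it limits the point. The ITT, the +56-day and the per-protocol analyses all keep deaths that occur 1 to 6 days after an injection. Section 8.3.5 gives the on-treatment analysis no role in the testing scheme.

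**A reader might infer a biased hazard ratio or a worthless analysis.** The documents support neither. The 6/7 comes from the dosing interval, which is the same in both blinded arms. If both arms lose the same fraction and the effect is similar across components, the hazard ratio need not be biased. The illustrated power of 62% to 87% means lost precision, not an uninformative analysis. What the analysis cannot do is speak for MACE with cardiovascular death included.

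**Conclusion.** The point holds as a moderate error confined to the on-treatment sensitivity analysis. About 6/7 of fatal first MACE in patients still dosing weekly (75% to 90% over the permitted intervals), and most events after which dosing never resumes, fall after censoring. What remains largely reflects non-fatal MI and stroke.

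The 6/7 assumes deaths spread evenly over the dosing interval and same-day events counted; the variants tried with weekly dosing move it up, not down. The figure of 9% to 34% of on-drug events lost depends on an assumed fatal share and is an illustration only. Larger losses can be produced by also assuming that some non-fatal events end dosing, but the documents give no figure for that either.

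It would be tempting to call this a defect that must be repaired before the trial can conclude. That goes too far: inference for the primary objective rests on the ITT population, and the formal non-inferiority decision is the same with or without this rule.

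**What to change.** In Section 8.3.2 (and in the RAP), define the on-treatment period for all subjects as first dose, or randomisation, to last dose date plus at least one dosing interval, capped at death or the last date on which MACE status is known. An event within that period counts. Seven days is the minimum; ten days also covers the 3-day late-dose window in Section 5.1. A skipped dose can leave a gap of 14 days, part of which a 10-day extension still misses; the +56-day analysis covers that case and should be kept unchanged.

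Reword the lead-in so that it no longer confines the list to subjects lost to follow-up, and state that the definition governs both event counting and censoring in Section 8.3.6.1.

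The cost is a sentence or two and no new data. The one drawback is that a few days after a true discontinuation are counted as on-treatment, which is minor given the half-life of about 5 days.

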3.3. Discussion of Design

This study is a clinical outcomes trial required by FDA as a post-marketing requirement to evaluate cardiovascular safety. It will provide important information regarding the cardiovascular safety and metabolic effects of albiglutide treatment of subjects with type 2 diabetes. Sufficient MACE events must be observed during the study to permit the assessment of cardiovascular safety. Consequently, to enter the study subjects must have established cardiovascular disease as well as type 2 diabetes. The study is powered on a predefined number of clinical events, consequently the number of subjects required and study duration may vary from that stated in the protocol.

This will be a double-blind, placebo-controlled study. All subjects will receive placebo or albiglutide in addition to usual standard of care for type 2 diabetes and cardiovascular disease, in order to assess the effect of albiglutide above that of currently available therapies alone.

The primary cardiovascular comparison will be to assess whether albiglutide is non-inferior to placebo with respect to time to first MACE. Missing data may inappropriately bias comparison towards declaring non-inferiority. The longer the duration of a study, the more difficult it is to avoid loss to follow-up and other sources of missing data. The product of the projected duration of this study and the number of subjects to be studied is intended to minimize the risk of missing data whilst still permitting the assessment of the safety of albiglutide to be over an appreciable period of time. Every effort will be made to keep subjects on their assigned study medication according to the protocol. Subjects who stop study medication will be followed throughout the whole study duration. More details about procedures for subject follow-up are provided in Section 4.5.

Phase III studies confirmed the glycaemic efficacy of both 30 mg and 50 mg doses of albiglutide, and both were generally well-tolerated. Although the 30 mg dose was effective at controlling glycaemia for at least 2 years in many subjects with type 2

diabetes, an increase in dose to 50 mg weekly offered additional benefit without significant safety issues (See IB for further details).

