5.7. Treatment after the End of the Study

Following the final study visit subjects will be contacted by telephone 5 ± 1 weeks after last dose of study medication to assess any AEs ongoing since the last visit or newly emergent.

Subjects will be treated as deemed appropriate by the investigator following the end of the study. Investigational product will not be provided to subjects by GSK after the end of the study.

The half-life of albiglutide is approximately 5 days, and significant therapeutic concentrations can persist for 3 to 4 weeks after discontinuation. The choice of other medicinal products and dose selection should be considered accordingly, as adverse reactions may continue and efficacy may, at least partly, persist until albiglutide levels decline.

The investigator is responsible for ensuring that consideration has been given to the post-study care of the subject's medical condition whether or not GSK is providing specific post study treatment.

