6. STUDY ASSESSMENTS AND PROCEDURES

The schedule of study assessments is shown in [Table 1](#). Detailed procedures for each assessment are provided in the SRM.

Table 1 Time and Events Table

| Procedures ^{1,2} | Screening ³ | Randomization ³ /Baseline (can be same day as Screening Visit) | Study Drug Check Phone Call (4-6 wks post rand.) | Clinic Visit Month 4 ± 18 days then every 8 months ± 18 days throughout the study | Unscheduled dose adjustment visit (if warranted) | Clinic Visit Month 8 ± 18 days then every 8 months ± 18 days throughout the study | Final study clinic visit ⁴ (or early withdrawal) | Follow up Phone Call 5 ± 1 weeks after last IP dose |
|--|------------------------|--|---|--|---|--|--|---|
| Written informed consent | X | | | | | | | |
| Review of Inc/excl criteria | X | X | | | | | | |
| Demography & directed medical history | X | | | | | | | |
| Assessment of MACE and micro-vascular events | | | | X | | X | X | |
| HbA1c | X ⁵ | | | X | | X | X | |
| Serum creatinine (eGFR) | X ⁵ | | | | | X | X | |
| Liver Function Tests ⁶ | | X | | | | X | X | |
| Genetic sampling ⁷ | | X | | | | | | |
| Patient reported outcomes questionnaires ⁸ | | X | | | | X | X | |
| Key concomitant non-diabetes medication | | X | | X | | X | X | X |
| Diabetes medication | | X | | X | | X | X | X |
| Study drug reminder | | | X | X | X | X | | |
| Physical examination ⁹ | | X | | | | X | X | |
| SAEs, AEs of special interest, AEs leading to IP discontinuation | | X | X | X | X | X | X | X |
| Pregnancy test ¹⁰ | X | X | | | | | | |
| Study drug dispense/compliance ¹¹ | | X | | X | X | X | X | |

- Subjects who discontinue investigational product should be handled as described in Section 4.4 and Section 4.5.
- Assessments per the Month 4 visit will alternate with those per the Month 8 visit throughout the study i.e., assessments at months 4, 12, 20 etc will be per Month 4; those at month 8, 16, 24 etc..will be per Month 8.
- Screening and Randomisation can occur at the same visit if all eligibility information is available. If Screening and Randomisation occur at the same visit assessments should not be duplicated.
- Once it is projected that the target number of MACE events will have been collected, a 3 month window will be defined for conducting the final, face to face visit.

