6.2.1. Cardiovascular Events

Events referred to the CEC by the investigator as potential endpoints or transient ischemic attacks (TIAs) will not be collected or reported as SAEs, regardless of the adjudication outcome ([Section 6.2.2](#)). These events will be reviewed by an Independent Data Monitoring Committee ([Section 9.8](#)).

The CEC will review and adjudicate the following clinical events:

- Myocardial infarction
- Stroke
- Unstable angina requiring hospitalization
- Hospitalization for heart failure
- Sudden cardiac death
- TIA
- In addition, all clinical events submitted for adjudication and all other SAEs with a fatal outcome will be reviewed and adjudicated to classify the cause of death as cardiovascular or non-cardiovascular.

When the local investigator reported event and the CEC decision on the nature of the event differ, the CEC's decision will be considered final. The detailed descriptions of the endpoint (and TIA) definitions necessary for adjudication are contained within the CEC Charter (available on request). The guiding principle will be the "2014 ACC/AHA Key Data Elements and Definitions for Cardiovascular and Stroke End Point Events for Clinical Trials" [ACC/AHA, 2014] and the "Third Universal Definition of Myocardial Infarction" endorsed by the European Society of Cardiology (ESC), the American College of Cardiology Foundation (ACCF), the American Heart Association (AHA), and the World Heart Federation (WHF) [Thygesen, 2012].

Source documentation required to support the adjudication of the events is described in the SRM. Recording of potential endpoint and TIA events in the eCRF and submission of source documentation will be required for clinical events meeting reporting criteria whether or not an endpoint event is suspected by the investigator.

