6.2.2. Adverse Events (AE) and Serious Adverse Events (SAEs)

The definitions of an AE or SAE can be found in [Appendix 5](#).

The investigator or site staff will be responsible for detecting, documenting and reporting events that meet the definition of an AE or SAE.

For this study events of myocardial infarction, stroke, unstable angina requiring urgent revascularization, hospitalization for heart failure, TIA and sudden cardiac death will not be collected or reported as AEs or SAEs. These events will be collected separately, subjected to blinded adjudication by an independent CEC using prespecified diagnostic criteria, and reported separately (Section 6.2.1.1). All other events that meet serious criteria as defined in [Appendix 5](#) should be reported as SAEs.

All events with an outcome of death will be adjudicated to classify the cause of death as specifically cardiovascular or non-cardiovascular. Any event resulting in death should be reported as a SAE unless the event is myocardial infarction, stroke, unstable angina w/ urgent revascularization, Heart failure, TIA or sudden cardiac death which the protocol specifies are not to be collected as adverse events.

The study will not collect all non-serious AEs. Non-serious AEs leading to discontinuation of investigational product and non-serious AEs of special interest (see Section 6.2.3) will be collected.

Any events not specifically addressed above should be reported as an AE or SAE according to the definitions in [Appendix 5](#).

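### The on-therapy censoring rule (last dose + 56 days) has no cap at death or last known MACE status, so a sensitivity analysis can count unascertained time as event-free

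*Protocol*

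**What the plan says.** Section 8.3.2 lists censoring dates for time-to-event data. Its lead-in reads "censoring time for subjects who lost to follow-up is defined as following". In the primary analysis such subjects are "censored at the date of last evidence of confirmatory status for MACE events", and the mortality bullet uses the last date the subject is known to be alive. Both of these dates are tied to observation. The on-therapy bullet is not: "For on-therapy analysis (on-treatment+56 days), censoring date will be the last dose date+56 days". Section 8.3.1 gives the per-protocol analysis a similar window, running to discontinuation of investigational product plus 56 days.

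Section 8.3.6.1 makes the on-therapy analysis a sensitivity analysis that repeats the primary set of outputs. These include incidence per 100 person-years and the absolute risk difference per 100 person-years.

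On ascertainment, the Table 1 row in Section 6 is "Assessment of MACE and micro-vascular events | | | | X | | X | X". The ticks fall at the Month 4-type, Month 8-type and final visits; the follow-up call has none. Section 5.7 times that call: "Following the final study visit subjects will be contacted by telephone 5 ± 1 weeks after last dose of study medication". For subjects who come off drug early, Section 3.3 says "Subjects who stop study medication will be followed throughout the whole study duration".

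The same on-therapy bullet stands in the initial protocol text and in the Amendment 1 text. The Amendment 2 list of changes in Appendix 9 does not edit Section 8.3.2.

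**The concern.** Time at risk should be counted only while an event could have been recorded. A subject who doses up to the final visit gets 56 further days at risk under the rule, but the last scheduled MACE assessment is at that visit and the last contact of any kind is at day 28 to 42. A subject lost while on drug can be credited with up to 56 event-free days after contact ended. A subject who dies of a non-cardiovascular cause on drug stays at risk after death.

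The adverse-event check at the closing call does not clearly fill the gap. Section 6.2.2 takes myocardial infarction and stroke out of adverse-event collection, in a sentence that ends "TIA and sudden cardiac death will not be collected or reported as AEs or SAEs".

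At stake are the person-year denominators of the on-therapy and per-protocol analyses, and hence their rates and absolute differences.

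**Working it through.** **1. The plan's own figures.** Section 8.2.1: margin 1.3, true hazard ratio 1.0, one-sided 0.025, power 90%, allocation 1:1. Events = 4 × (1.960 + 1.2816)² / (ln 1.3)² = 42.03 / 0.06884 = 610.6, so 611, as stated. Mean follow-up = 611 / 9400 / rate = 3.25 years at 2% and 2.17 years at 3%, in line with the stated 3.2 and 2.2. Total person-years (PY) are 611 / 0.02 = 30,550 and 611 / 0.03 = 20,367.

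**2. Unobserved days per subject.**
- Dosing weekly up to the final visit (last dose taken as 0–7 days before it): 56 − 7 = 49 to 56 days without scheduled MACE assessment.
- Same subject, if the closing call is credited with capturing events: 56 − 42 = 14 to 56 − 28 = 28 days.
- Stopped drug less than 56 days before the final visit: the part of the window that runs past that visit.
- Stopped drug at least 56 days before the final visit and stayed in follow-up: 0 days. The Amendment 2 schedule for these subjects assesses MACE at the 4-monthly contacts and the final visit.
- Lost while on drug: up to 56 days.

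**3. If the bullet covers completers.** Extra PY = 9400 × share on drug at end × days / 365.25. The documents do not give the share, so 60–80% is an assumption and 100% is a ceiling.

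| Share on drug | Days | Extra PY | % of 30,550 | % of 20,367 |
|---|---|---|---|---|
| 60% | 49–56 | 757–865 | 2.5–2.8 | 3.7–4.2 |
| 80% | 49–56 | 1009–1153 | 3.3–3.8 | 5.0–5.7 |
| 100% | 49–56 | 1261–1441 | 4.1–4.7 | 6.2–7.1 |
| 60% | 14–28 | 216–432 | 0.7–1.4 | 1.1–2.1 |
| 80% | 14–28 | 288–576 | 0.9–1.9 | 1.4–2.8 |

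These denominators are full follow-up. On-therapy time is shorter, so the percentages on that base are somewhat larger.

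**4. If the bullet covers only subjects lost.** Section 8.2.1 assumes loss of 1% or less, so at most 94 subjects: 94 × 56 / 365.25 = 14.4 PY, which is 0.05% of 30,550 or 0.07% of 20,367.

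**5. Hazard ratio and rates.** A Cox simulation (300 replicates, N = 9400, 2-year accrual, study length 3.2 years at 3% and 4.4 years at 2% from Table 2) compared the rule as written with a cap at the final visit. Drug discontinuation was assumed at 12% per year in both arms, or 15% on albiglutide against 10% on placebo. This left 66–77% on drug at the end.
- Person-time rose by 3.3% (2% rate) or 5.5% (3% rate), relative to capped on-therapy time.
- With a true hazard ratio of 1.0 and equal discontinuation, the placebo rate fell from 2.996 to 2.839 and from 2.002 to 1.938 per 100 PY.
- With a true hazard ratio of 1.3 and equal discontinuation at the 3% rate, the absolute difference fell from 3.867 − 2.991 = 0.876 to 3.665 − 2.834 = 0.831 per 100 PY, a reduction of 5.1%.
- The hazard ratio moved by 0.0002 or less in every scenario, including unequal discontinuation and a true hazard ratio of 1.3.

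The simulation did not model loss to follow-up or non-cardiovascular death. The documents give no rate for such deaths, so the missing cap at death is not sized here beyond 56 days per death.

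**The case against.** **Scope.** The lead-in names subjects lost to follow-up, and the list gives no censoring date for completers. On that reading the excess is about 14 person-years and trivial, and handling of completers may be settled in the analysis plan, which is not shown. This stands as a limit on size: the 2.5–6% depends on applying the bullet generally. It does not rescue the rule, which goes past observed time on either reading.

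**Ascertainment.** The closing call asks about newly emergent adverse events, potential endpoints must be recorded even when the investigator does not suspect one, and under Section 6.2.1 "all other SAEs with a fatal outcome will be reviewed and adjudicated". Some events, fatal ones above all, could therefore surface at the call. This is fair, and it is why the 14–28 day rows are shown. Nothing is scheduled after day 42 in any case.

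**Early discontinuers.** Their 56 days fall inside continued follow-up unless they stop close to the final visit or are lost. This stands fully. It would be wrong to say that the whole 56-day window goes unobserved in general.

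**Non-inferiority.** A reader might infer that uncounted events pull the comparison towards no difference, the bias that Section 3.3 warns about. The documents do not support that here. Non-inferiority is tested on the Cox hazard ratio in the ITT population, where censoring is at last evidence of MACE status. Even in the on-therapy analysis, adding similar event-free time at the end of follow-up lowers both arms' rates and leaves their ratio where it was.

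**Conclusion.** The point holds in a limited form. The on-therapy rule is stated, not left open, and it lacks the tie to observed status that the primary and mortality bullets in the same list have. It gives wrong person-time for subjects lost while on drug and, if applied generally, for those still dosing at or within 56 days of the final visit.

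The size depends on the reading. Applied to completers with 60–80% on drug at the end (assumed), rates and absolute differences per 100 person-years are diluted by about 2.5–6%, or about 1–3% if the closing call captures events. Applied only to subjects lost, at 1% or less, the effect is under 0.1%. Only the on-therapy sensitivity analysis and the per-protocol 56-day window are involved. The hazard ratio, the non-inferiority conclusion and the 611-event target are essentially unaffected.

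**What to change.** In Section 8.3.2, censor the on-therapy analysis at the earliest of last dose + 56 days, death, and the last date on which MACE status is known. State that this applies to all subjects without an event, not only those lost to follow-up. Put the same cap on the per-protocol window in Section 8.3.1.

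Optionally, record MACE status at the existing 5 ± 1 week call (one more tick in Table 1 and in the schedule for subjects who discontinue), so that more of the window is observed.

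The cost is a sentence in each section, with no change to treatment, sample size or the primary analysis. The optional step adds one question to a call already planned.
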